6.3.4 Re-screening

Patients who do not meet the eligibility criteria at telephone screen or baseline may be eligible for rescreening. For example, those who are currently receiving a course of therapy could be rescreened once this course has ended. Patients who do not meet the BDI-II or ICD-10 criteria at baseline could be offered a rescreen as long as one month had elapsed since their original baseline appointment. The telephone screening questionnaire would also be repeated in order to identify any other changes since the original screen, which could make them unsuitable to take part. Ineligible patients would be advised that they can re-contact the study team to request one rescreen, as long as one month had elapsed since the original screen, and the study was still recruiting.

6.4 Consent

Prior to commencing the baseline assessment, the researcher will obtain written informed consent from the patient relating to their participation in the trial. Informed consent will be obtained either via an online consent 'e-consent' method, or via paper-based informed consent.

Paper-based informed consent will be used if the researcher is meeting with the patient in-person and this option is preferred, or if the patient wishes to complete the baseline via telephone call and is not able to complete an electronic consent. If paper consent is required, two copies of the consent form will be sent to the participant with a pre-paid envelope. The patient will complete both forms

and return them to the local researcher to countersign. The participant will then be sent one of the fully signed forms for their records.

Patients completing the assessment via e-consent will receive an electronic copy of their e-consent form via email. A copy will also be sent to the patient's GP if they are eligible to take part in the study.

Participants will be reminded that they are free to withdraw from the trial at any time without giving reason and without prejudicing their further treatment. We will seek consent to use data collected up to the point of withdrawal, and this will be explained in the information sheet. In addition, in line with open access data requirements, information may also be used to support other research in the future and may be shared anonymously with other researchers. This will be explained in the information sheet.

Consent will also be sought for details of the participant to be shared with the qualitative researcher so that they can be approached about taking part in an interview. Taking part in an interview will be optional. Full details of the integrated qualitative research are detailed separately; see Section 6.15.

As part of the baseline consent procedure, patients who give informed consent for trial participation will be asked to indicate whether they would be willing to be contacted about future related research. All participants will also be asked to provide (optional) consent for the research team to access their medical records in order to collect data on treatments and consultations in primary care. Intervention participants will be asked for their (optional) consent for the research team to have access to their EMDR therapy notes from their time in the study, and for audio-recordings of their EMDR sessions to be used for research purposes.

6.5 Randomisation

Individuals will only be randomised after: (a) written informed consent (wet ink or eConsent) has been received; (b) baseline assessments have been completed; and (c) eligibility is confirmed by the local researcher.

The randomisation sequence will be generated by Sealed Envelope[™]. Randomisation will be stratified by centre and minimised on baseline antidepressant use (Yes; No) and depression severity (baseline (BDI-II score): 14-27; 28-36; 37-63). Stratifying by centre will ensure a balance in terms of local differences and proportionate workload for therapists. The minimisation variables are important prognostic indicators and hence minimising will ensure a balance between the two groups. Participants will be randomised to one of two treatment groups on a 1:1 ratio, that is either EMDR therapy in addition to usual care (intervention arm) or usual care (control arm). The researcher will inform the participant of the allocation during the baseline appointment where possible, or by telephone/email shortly afterwards.

The local researcher will sign into the secure online randomisation system, find the individual's (participant's) unique record and enter the necessary minimisation variables; they will then receive confirmation of the randomised allocation (EMDR or UC). The local research team will inform the EMDR therapist if a patient has been allocated to them. Confirmation of the participant's treatment allocation will be emailed to the local researcher at the coordinating centre and the University of Bristol study mailbox, for the attention of the Trial Manager. The allocation will be recorded on the trial database. The local research team will send written confirmation of the allocation to the participant's GP.

6.6 Embedded Mechanistic Study

The embedded mechanistic study will determine whether reductions in depression are mediated by key memory-processing mechanisms and if working memory capacity is associated with treatment response. The specific objectives were set out in section 4.6.

6.6.1 Mechanistic Measures

Potential mediators will be measured during treatment at 16 weeks post-randomisation:

- 1) VAS (0-10) for vividness and emotional intensity of depression-related memories;
- 2) number, and strength, of negative self-beliefs; and
- 3) symptoms of re-living, avoidance and hyper-arousal linked to past distressing events.

The timing of 16 weeks allows: (1) time to start therapy after randomisation (mean: 3 weeks in previous trials [30, 44]; (2) session cancellations by patients; and (3) the processing phase of EMDR to begin (phase 4 of 8). In a trial of a similar length intervention (12-18 sessions) [30], by 12 weeks participants had only had an average of 5 sessions.

To determine whether reductions in depression are mediated via key memory-processing mechanisms, it will be necessary to ask individuals to provide brief details about the past stressful experience that they associate (most strongly) with their depression at baseline. They will be prompted to think about this memory when they are rating the vividness and emotional intensity of depression-related memories at 16 weeks. Similar scales have been used previously in studies examining the WM hypothesis [22].

The number, and strength, of negative self-beliefs will be measured based on a list of negative and positive cognitions in the EMDR manual [19]. Symptoms of re-living, avoidance and hyper-arousal will be measured using the ITQ [58]. Repeat measurements at 26 weeks will enable mediation analyses of 52 week outcomes. We will examine the test re-test reliability of the list of negative self-beliefs by asking participants to repeat those questions at one of the follow-up appointments (either 26 or 52 weeks).

Memory vividness depends on the detail, sharpness and strength with which memories are being actively represented and processed in WM [59]. EMDR is thought to reduce the resources available for detailed memory representation and processing by using up both visuospatial and processing resources. The amount of WM resources available for vivid memory representation depends on both the individual's capacity in the first place, and the fraction of the resource taken up by EMDR. If WM capacity is large, then EMDR is unlikely to lead to sufficient reduction in WM to prevent distressingly vivid reconstruction.

WM capacity will be measured at baseline using a short (15 - 30 minutes) battery of standardised measures. Two aspects of WM capacity are most likely to be relevant: visuospatial capacity, and processing capacity. Visuospatial capacity will be measured using a spatial memory 'Corsi' task where individuals are shown a pattern of blocks on a screen. A spatial sequence of these blocks illuminates, which they then need to recreate. The capacity of spatial WM is determined by performance at increasing sequence lengths. Processing capacity will be measured using an N-back task where individuals have to recall letters in a constantly changing string of single letters on a screen. The individual has to indicate if a given letter is the same as the letter N trials earlier. We will assess how well individuals perform at increasing N to determine their maximal N. Finally, we will examine to

what extent the effects of objective WM capacity might be captured by subjective memory capacity by asking participants a short set of questions about their memory.

6.6.2 Sample size: Primary mechanistic hypothesis

We used the methods by Vittinghoff and Neilands [60], implemented using the R package medssp, to estimate the power to detect mediation of the intervention effect by a standardised continuous post-randomisation measure of the mediator (e.g. visual analogue scale) assuming: a standardised total effect of 0.378 (based on the MCID as stated above); no exposure-mediator confounding (given the intervention will be randomised); moderate confounding for the mediator-outcome association (correlation of 0.3); and a medium standardised effect size (square root of R2 = 13%) for the exposure-mediator association. For a sample size of 285 (based on 25% attrition), we have 87.2%, 87% and 79.4% power to detect an indirect effect of 40%, 30% and 20% respectively.

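### The mediation power in 6.6.2 and the R2 = 13% given for the exposure-mediator effect are on different scales: the stated powers correspond to an R2 of about 3%

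*Protocol*

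**What the plan says.** Section 6.6.2 is the only power statement for the primary mechanistic objectives in 4.4.1. The method is given as "We used the methods by Vittinghoff and Neilands [60], implemented using the R package medssp"; the title of reference 60 shows that this is a joint test of the indirect effect. The inputs are:

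- total effect: "a standardised total effect of 0.378 (based on the MCID as stated above";
- treatment to mediator: "a medium standardised effect size (square root of R2 = 13%) for the exposure-mediator association", with "no exposure-mediator confounding (given the intervention will be randomised";
- mediator to outcome: "moderate confounding for the mediator-outcome association (correlation of 0.3";
- sample: "For a sample size of 285 (based on 25% attrition".

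The result is "we have 87.2%, 87% and 79.4% power to detect an indirect effect of 40%, 30% and 20% respectively". Section 6.5 sets 1:1 allocation. Section 5.8.4 gives a two-sided 5% level for the efficacy sample size; 6.6.2 gives no level of its own.

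**The concern.** The square root of an R2 is a correlation. For a two-arm trial with equal allocation, a correlation of 0.36 between arm and mediator is a difference of about 0.72 mediator SDs between arms, twice 0.36. The parenthesis in 6.6.2 therefore points to one input and the words before it (a standardised effect size) can be read as another.

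The choice matters because the total effect is fixed at 0.378. The indirect effect is the product of the two paths. For a given proportion mediated, doubling the treatment-to-mediator path halves the mediator-to-outcome path, and the joint test then depends on detecting that smaller second path. A reader who takes R2 = 13% at face value would believe that a mediator carrying 20% of the effect is detected with nearly 80% power, which that assumption does not deliver.

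**Working it through.** **Inputs.** n = 285 (380 × 0.75), total effect T = 0.378 and confounding correlation 0.3, all from 6.6.2. The proportions mediated are 40%, 30% and 20%, so the indirect effects are 0.1512, 0.1134 and 0.0756. Allocation is 1:1 (6.5), so a 0/1 arm indicator has SD 0.5. Two-sided 5% is assumed by carrying it over from 5.8.4. √0.13 = 0.3606.

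**Formulas.** Write a for the between-arm difference in mediator SDs and r = 0.5a for the arm-mediator correlation, so that R2 = r². Mediator and outcome have SD 1.

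- Path a: z_a = r√n / √(1 − r²)
- Path b: b = proportion × T / a, and z_b = b√[n(1 − r²)(1 − 0.3²)]
- Joint power = Φ(z_a − 1.96) × Φ(z_b − 1.96)

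**Step 1: reproduce the stated figures, with a = 0.3606.** Here r = 0.1803 and R2 = 0.3606²/4 = 3.25%. z_a = 3.09, so path a has power 0.872. The multiplier for path b is √(285 × 0.9675 × 0.91) = 15.84.

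| Mediated | b | z_b | Path b power | Joint power | Stated |
|---|---|---|---|---|---|
| 40% | 0.419 | 6.64 | 1.000 | 87.2% | 87.2% |
| 30% | 0.315 | 4.98 | 0.999 | 87.1% | 87% |
| 20% | 0.210 | 3.32 | 0.913 | 79.6% | 79.4% |

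Agreement is within 0.2 points. The plateau near 87% is the power of path a alone, which caps the joint test.

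**Step 2: R2 = 13%.** Here r = 0.3606 and a = 0.7211. z_a = 6.53, so path a has essentially 100% power and no ceiling near 87% can arise. The multiplier is √(285 × 0.87 × 0.91) = 15.02.

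| Mediated | b | z_b | Joint power | Stated |
|---|---|---|---|---|
| 40% | 0.210 | 3.15 | 88.3% | 87.2% |
| 30% | 0.157 | 2.36 | 65.6% | 87% |
| 20% | 0.105 | 1.57 | 35.0% | 79.4% |

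**Step 3: robustness.** Keeping the 0.3 confounding, other reasonable forms of the formula (residual or total SDs, with or without the term for treatment-mediator collinearity) give 88–94%, 66–74% and 35–41% under R2 = 13%. A simulation of the joint test (6,000 runs per cell) gives 90%, 67% and 36%. The same simulation at a = 0.3606 gives 88%, 86% and 81%, in line with the stated values.

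**Step 4: other readings.** Treating arm as a variable with SD 1 and coefficient 0.36 gives 100%, 99.7% and 88.3%. Reading the parenthesis as a correlation of 0.13 gives about 60% throughout. A one-sided 5% test with R2 = 13% gives 93%, 76% and 47%. None of these matches.

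**The case against.** The strongest reply is that nothing was miscalculated. Section 6.6.2 names a standardised effect size, and the total effect of 0.378 in the same sentence is a between-arm difference divided by an SD (5.8.4). Entering 0.36 on that same scale is coherent, and it returns the stated powers. On this view the R2 is only an aside on where 0.36 came from, and the protocol nowhere says in words that treatment explains 13% of mediator variance. A 0.72 SD shift would also be nearly twice the trial's own target effect, so 0.36 SD is at least as plausible an intention.

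Most of that stands. It means a reader should not infer that the power calculation itself is wrong, that all three powers fail (the 40% figure does not), or that the 20% figure is about twice a true value. The last would require R2 = 13% to be the intended input, and the protocol does not settle that. Nor does the protocol say that a non-significant mediator will be taken as evidence against mediation; 10.1.2 plans several estimation methods and sensitivity analyses.

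What the reply does not remove is the mismatch. With 1:1 allocation, 0.36 SD is not the square root of the exposure-mediator R2, so the parenthesis and the 30% and 20% powers cannot both be right.

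**Conclusion.** The point holds as an inconsistency of scale. Of the readings tried, only a 0.36 SD between-arm difference yields the stated powers, and that is an R2 of about 3%, a quarter of the 13% written. If 13% was meant, the power for 30% mediated falls from 87% to about 66% (66–74% across formula variants) and for 20% from 79.4% to about 35% (35–41%); the 40% figure is not materially changed.

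This rests on the joint test, a two-sided 5% level carried over from 5.8.4, and closed-form and simulation checks rather than a run of the named package. The target of 380 was set on the BDI-II in 5.8.4 and does not depend on this paragraph, and the efficacy analysis is untouched. The severity is moderate: the paragraph needs correcting because it is the sole power claim for the primary mechanistic objectives, but the design does not change.

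**What to change.** In 6.6.2, state the exposure-mediator effect on one scale and make the powers match it. There are two options:

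- describe it as a 0.36 SD between-arm difference in the mediator (R2 about 3%) and keep the three powers; or
- keep R2 = 13% (about 0.72 SD) and restate the powers from a rerun of the package, expected at about 88%, 66% and 35%.

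Preferably show both as a small grid. With the total effect fixed, power for 20–30% mediation falls between these two values as the treatment effect on the mediator rises, and a single scenario hides this. State the significance level used as well.

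The cost is rewording one paragraph and rerunning existing code. No extra participants are needed, though the second option would show less favourable power.

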6.7 Emergency contact procedure for participants

The participant's GP will retain clinical responsibility for them throughout their participation in the trial. Details of what a participant should do if they experience any problems or adverse effects whilst taking part in the trial is detailed in the PIL.

If a symptom is troublesome (as explained in the PIL) participants are advised to seek medical help in the normal way (e.g., dialling 111 or contacting their GP). In an emergency they should phone the emergency services or attend an Emergency Department. There will also be information provided about helplines participants can choose to access for mental health support 24/7, which will be available on the study website, or on paper if required.

Participants receiving EMDR will complete a measure of depressive symptoms (PHQ-9) for each session which will be shared with their therapist. This will completed via REDCap survey shortly ahead of the session, or completed in person at the beginning of each session. If this is completed on paper, the therapist will enter this into the database following the therapy session. A safety protocol outlines the procedure to follow if a therapist is concerned about the risk, such as increased suicidality. Further details on the safety protocol are outlined in section 7.1.

6.8 Schedule of assessments and data collection

Table 2 specifies the timepoints for outcome data collection. All timepoints are counted from randomisation.

Table 2: Schedule of assessments and research data collection

	Pre-baseline	At randomisation		STUDY PERIOD Post-randomisation					
Data collection timepoint	Identification /Screening	Baseline Appointment	2 weeks	8 weeks	16 weeks	26 weeks	39 weeks	52 weeks	End of study
ENROLMENT:									
EOI Form	•								
Phone Screen	•								
Informed consent		•							
Socio-demographics		•							
CIS-R		•							
History of depression and treatment History of		•							
stressful/traumatic experiences and willing		•							
to work on memories		• A							
LEC-5 CTQ		• A							
Life Events checklist		• A							
Stressful experience		•"							
linked to depression (description and age at event)		• ^A							
Social support		• A							
Long-term health conditions		● ^A							
Self-report memory		• ^A							

Cognitive (working memory) tasks Reasons for taking part Future contact	• A • A						
Consent to pass	• ^A						
information to GP							
Random allocation	• ^A						
INTERVENTION:							
EMDR Sessions*B		-			→		
PHQ9, SUDs and VOC*B		←			→		
ASSESSMENTS:							
BDI-II (primary outcome)	•				•		•
PHQ-9	● ^A	•	•	•	•	•	•
GAD-7	• A	•	•	•	•	•	•
Global rating of change			•	•	•	•	•
Negative self-beliefs	• A		•	•	•	•	•
ITQ (shortened)	• A		•	•	•	•	•
Vividness/Intensity of	• A		•	•	•	•	•
memories	^						
Grounding question	• ^A		•	•	•	•	•
Your EYE-D EMDR	• ^B						
therapy Antidepressant	_ A		•	•		•	•
medication	•		•	•	•	•	•
WSAS	• A				•		•
EQ-5D-5L	• ^A				•		•
ICECAP-A	• ^A				•		•
Other treatments				_		_	
received (cCBT/talking			•	•	•	•	•
therapy)							

Use of healthcare
services (ModRUM)
Medical note data
collection

^{*}Time period is an approximation of when EMDR sessions are expected to take place; AOnly completed if patients are eligible at this point BIntervention group only

6.9 Blinding and unblinding

Given the nature of the intervention, it will not be possible to blind participants to treatment allocation. Self-reported outcomes will avoid observer bias.

The wider Trial Management Group (TMG) will be blinded to aggregate data by treatment group with only the reporting of follow-up rates presented to the TMG by arm. This is to monitor potential discrepancies in follow-up rates. The site and clinical site leads, one of the two trial statisticians and trial/data management staff from the University of Bristol, trial therapists and supervisors of trial therapists will be unblinded for practicalities of delivering the trial and intervention. Two statisticians based at the University of Bristol will support this trial. The senior (lead) statistician will be blinded throughout the trial. The second trial statistician will perform all disaggregated analyses according to a pre-specified SAP and will attend closed Data Monitoring Committee (DMC) meetings as required. Clinicians (Pls), other researchers and centre staff will not be blinded.

6.10 Change in participation status

Participants can choose to withdraw for any reason at any time during their involvement in the trial. Participants can withdraw from: (a) EMDR sessions, and/or (b) providing data to the trial, at any time for any reason without affecting their usual care. Clinical site leads can also decide to withdraw participants based on clinical opinion at any time during the trial. A participant may be discharged from treatment by their therapist if they do not engage with therapy.

Where possible, any data collected up to the point of withdrawal will be retained for analysis, as advised in the PIL. Participants who withdraw from a) EMDR sessions, will be asked if they are still willing to provide follow-up data and/or take part in a qualitative interview if applicable. If a participant withdraws from b) providing data to the trial, no further data will be collected – this includes the collection of health resource use data from the patient's medical notes at the end of the trial. They will not be approached for future follow-up questionnaires or qualitative interviews.

Withdrawals will be recorded on the REDCap database, including reasoning for withdrawal, if provided.

Participants who commence concurrent psychological therapy after randomisation to the intervention arm will **not** be withdrawn from the intervention or study by the trial team, though they would be advised against commencing concurrent therapy. Participants in the intervention arm will **not** be withdrawn from the intervention or study due to lack of efficacy.

6.11 Retention strategies & participant payments

Participants will be followed up (by videocall or in person) at 26 and 52 weeks. Brief follow-ups (telephone/videocall) at 2 & 8 weeks will be used to maximise trial retention (as advised by PPI) and at 16 weeks to collect data on mediators and depressive symptoms. A brief 39-week follow-up will aid longer-term retention. At baseline, participants will be asked their preference for mode of contact for these follow-up appointments. They will also have the option of completing follow-up questionnaires online independently or by post.

If full questionnaire data collection is not feasible, the researcher will attempt to collect a measure of depressive symptoms (BDI-II or PHQ-9 as appropriate to the time point), current use of antidepressant medication, and receipt of other psychological treatments as a minimum.

If the researcher is unable to contact the participant for any of the follow ups, the researcher will send a brief postal questionnaire, or a link to an online version of the questionnaire.

Participant appointments will be confirmed by email or letter. If questionnaires are sent by post, a brief covering letter and pre-paid envelope will also be included. If patients do not respond to postal or online questionnaires within two weeks, a reminder letter, email or text will be sent. Up to 3 reminders will be sent in total.

Upon receipt of completed questionnaires at 8, 16 & 39 weeks, the central research team will offer participants a £10 gift voucher (i.e. £10 per time-point). £20 vouchers will be offered for the longer follow-ups at 26 & 52 weeks (£70 potential total). No vouchers will be offered for the initial 2-week follow-up as this will be a brief contact (phone/email) to check in and answer any questions that have arisen about participation, and record brief details of symptoms of depression/anxiety.

A £20 voucher will also be offered for taking part in a qualitative interview.

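### The single fallback dataset in section 6.11 does not protect any mediator at week 16, the time point on which the primary mechanistic objective rests

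*Protocol*

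**What the plan says.** Protocol section 6.11 describes the week-16 contact as being there "at 16 weeks to collect data on mediators and depressive symptoms". The next paragraph sets one fallback for all follow-ups, for use if the full questionnaire cannot be obtained: "collect a measure of depressive symptoms (BDI-II or PHQ-9 as appropriate to the time point), current use of antidepressant medication, and receipt of other psychological" (the last item is other therapy received). The list is described as a minimum that the researcher will try to obtain. Only the choice between BDI-II and PHQ-9 depends on the visit. Participants who cannot be contacted are sent a brief postal questionnaire or an online link. The protocol does not list what that form contains.

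Section 6.6.1 states: "Potential mediators will be measured during treatment at 16 weeks post-randomisation". It names three groups:

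- "VAS (0-10) for vividness and emotional intensity of depression-related memories"
- "number, and strength, of negative self-beliefs"
- "symptoms of re-living, avoidance and hyper-arousal linked to past distressing events", measured with the ITQ

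Section 4.4.1 ties the primary mechanistic objective to these 16-week measures, with depression at 26 weeks as the outcome. Section 6.6.1 assigns the 26-week repeats to mediation of 52-week outcomes. Section 6.6.2 gives the power: "For a sample size of 285 (based on 25% attrition"), it is 87.2%, 87% and 79.4% for indirect effects of 40%, 30% and 20%.

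**The concern.** A minimum dataset states what is protected when time or goodwill is short. At week 16 this one protects PHQ-9 and two treatment items and none of the three mediator groups, although section 6.11 itself gives the mediators as a reason for the contact. The list suits the 26- and 52-week efficacy visits but has not been adapted to week 16.

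A participant who gives only the minimum at week 16 counts as followed up but has no mediator value at the time point the objective needs. That leaves two routes: lose the participant from a complete-case mediation analysis, or impute the mediator. The first costs power against a sample size with no separate allowance for it. The second rests on added assumptions and recovers only part of the information. The loss could also be selective if fallback users differ in engagement or severity. That is plausible, but the documents do not show it.

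**Working it through.** **Is any mediator in the fallback?**

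| Item | In the 6.11 minimum at week 16? |
|---|---|
| PHQ-9 | yes |
| Antidepressant use | yes |
| Other psychological treatment | yes |
| Vividness and emotional intensity, two 0-10 ratings | no |
| Negative self-beliefs | no |
| Shortened ITQ | no |

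**Can another visit stand in?** In Table 2 the mediator rows carry a baseline mark and five follow-up marks, against six for PHQ-9, which I read as weeks 8, 16, 26, 39 and 52. A missing week-16 value therefore has baseline, week-8 and week-26 neighbours. Neither neighbouring follow-up replaces it. The 26-week value is concurrent with the outcome. Week 8 precedes the processing that 6.6.1 waits for: therapy started a mean of 3 weeks after randomisation in earlier trials, and in one of similar length participants averaged 5 sessions by 12 weeks.

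**Where 285 comes from.** Section 5.8.4 allows 25% attrition at 26 weeks: 380 × 0.75 = 285. No further allowance is made for people with a 26-week BDI-II but no week-16 mediator.

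**Reproducing the stated power.** Inputs from 6.6.2:

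- total effect 0.378
- exposure-mediator effect a = √0.13 = 0.361, read as a standardised difference (read as a correlation, it would give a-path power of about 100%)
- mediator-outcome confounding correlation 0.3
- 1:1 allocation (section 6.5); two-sided 5% assumed, as in the efficacy calculation

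Power for joint significance is the product of two path powers:

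- a-path: Φ(a√N / (2√v) − 1.96), with v = 1 − 0.13/4 = 0.9675
- b-path: Φ(b√(N × v × (1 − 0.3²)) − 1.96), with b = proportion mediated × 0.378/0.361 and outcome SD 1

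At N = 285 the a-path gives Φ(3.094 − 1.96) = 0.872. For a 20% indirect effect, b = 0.210 and the b-path gives Φ(3.321 − 1.96) = 0.913, so the product is 0.796. The b-path is about 0.999 at 30% and 1.000 at 40%. The results, 87.2%, 87.1% and 79.6%, agree with the stated 87.2%, 87% and 79.4%.

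**Effect of missing week-16 mediators.** The documents give no rate, so the share m of the 285 is an assumption, and complete-case analysis is assumed.

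| m | N = 285(1 − m) | SE factor 1/√(1 − m) | 40% | 30% | 20% |
|---|---|---|---|---|---|
| 0 | 285 | 1.00 | 87.2% | 87.1% | 79.6% |
| 5% | 271 | 1.03 | 85.5% | 85.3% | 76.8% |
| 10% | 256 | 1.05 | 83.5% | 83.3% | 73.8% |
| 15% | 242 | 1.08 | 81.4% | 81.1% | 70.4% |
| 20% | 228 | 1.12 | 79.0% | 78.5% | 66.7% |

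Power falls below 80% once fewer than 234 remain for the 40% effect (51/285, about 18% lost) and once fewer than 237 remain for the 30% effect (48/285, about 17% lost). For the 20% effect it starts just below 80%.

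**The case against.** A reader might infer that participants on the minimum drop out of the primary mechanistic analysis. The documents do not support that. No section states complete-case handling; section 10.1.2 names the parametric g-formula and structural equation models, and missing-data handling may sit in the SAP. PHQ-9 is kept, and the mediators are also scheduled at baseline and weeks 8 and 26, so imputation has material to work with. For the same reason it is too strong to say that the fallback secures repeatable items and gives up an unrecoverable one: the treatment items and the mediators are both asked again at 26 weeks. Someone who gives only the minimum at another visit can still have week-16 mediators and a 26-week BDI-II.

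The list is also a floor, so researchers may collect more. The brief form may carry the mediators. Section 6.11 offers a choice of contact mode, up to three reminders and a £10 voucher at week 16. Hard-to-reach people may overlap with the 25% already allowed for, so m must be read net of that overlap. Finally, requiring every mediator would restore most of the week-16 questionnaire and defeat the purpose of a fallback.

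All of this limits the size of the point and the remedy. It does not answer the narrower one: the stated priority list leaves out the mediators at the contact intended to collect them, and imputing a mediator does not restore what was not observed.

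**Conclusion.** The point holds in a limited form. The week-16 fallback does not protect the mediators, and the mechanistic sample may fall below 285 by an amount the protocol does not quantify. Only participants who give just the minimum at week 16 are affected. The stated power figures are correct for N = 285.

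With complete-case analysis and an assumed 10% of the 285 affected, power for the 40%, 30% and 20% indirect effects is about 84%, 83% and 74%. At 20% affected it is about 79%, 79% and 67%. Imputation would reduce the loss to an extent that cannot be computed from the documents. Bias from selective use of the fallback is possible, but its direction is not documented. This is a cheap improvement to a stated collection rule. It does not undermine the efficacy analysis.

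**What to change.** In section 6.11, make the minimum specific to the visit. At week 16, collect in this order:

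1. PHQ-9.
2. The two 0-10 ratings of vividness and emotional intensity, with the baseline memory prompt.
3. The existing antidepressant and other-treatment items.
4. If the participant is willing, the negative self-beliefs list and then the shortened ITQ.

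State that the week-16 brief postal or online form carries the mediator items. Leave the minimum at the other visits unchanged.

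This secures the first mediator group in the fallback and gives the other two a defined priority. It restores power only as far as participants complete the items. The cost is protocol wording, a reordered short form and perhaps a minute more for the two ratings, with a small risk that the last items are completed less often. It helps only week-16 contacts made after the change.
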